6.0 DATA MANAGEMENT

Data will be collected and retained in accordance with the Data Protection Act 2018. The data collected from the study will be entered in a study specific database by designated staff. The database will be kept on a secure NHS computer. Access to the database will be given to authorised personnel only and log of access will be kept in the study file by the Principal Investigator.

7.0 REGULATORY ISSUES

7.1 Ethics Approval

In view of the retrospective nature of this study, approval from a Research Ethics Committee within the UK Health Departments Research Ethics Service is not necessary. and Health Research Authority (HRA). The criteria for REC review exemption is:

Research involving previously collected, non-identifiable information

Research limited to secondary use of information previously collected in the course of normal care (without an intention to use it for research at the time of collection) is generally excluded from REC review, provided that the patients or service users are not identifiable to the research team in carrying out the research. This exception also applies to research undertaken by staff within a care team using information previously collected in the course of care for their own patients or clients, provided that data is anonymised or pseudonymised in conducting the research.

The study will be conducted in accordance with the recommendations for physicians involved in research on human subjects adopted by the 18th World Medical Assembly, Helsinki 1964 and later revisions.

7.3 Confidentiality

A unique reference number will be used to anonymize the details of all participants. The investigator must ensure that the patient's privacy is maintained at all times. On the Case Report Form (CRF) or other documents, patients will be identified by a study ID number only. The investigator shall permit direct access to study source document for the purposes of monitoring, auditing, or inspection by the Sponsor, authorised representatives of the Sponsor and Regulatory Authorities.

7.4 Indemnity

Imperial College London holds negligent harm and non-negligent harm insurance policies which apply to this study.

7.5 Sponsor

Imperial College London will act as the main Sponsor for this study. Delegated responsibilities will be assigned to the NHS trusts taking part in this study.

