3.2 Methods

Patients with a diagnosis of malignancy and SARS-CoV-2 infection will be identified from electronic medical records and entered into a pre-designed database.

Methodologically, this project will be limited to secondary use of information previously collected in the course of normal care (without an intention to use it for research at the time of collection). Every aspect of this project will be undertaken by staff within a care team using information previously collected in the course of care for their own patients.

Routinely collected clinical information including patients' demographics, prior medical history, cancer history including prior and current anti-cancer therapy, co-morbidities will be collected in a data collection proforma. Results of routinely collected blood tests, radiologic assessments and therapies received by the patient will also be entered onto the database. Clinical outcomes including response to treatment and patients' survival will be evaluated in relationship to baseline clinico-pathologic profile. Clinico-pathologic will be correlated to patient's outcome, in particular overall survival (OS) as derived from electronic medical records.

The database consists of a Microsoft Excel spreadsheet including the following variables: age, gender, smoking status, prior comorbidities (cardiovascular, diabetes, dementia, pulmonary and kidney disease, liver disease, hypertension, immunosuppression), histotype of malignancy, date of first cancer diagnosis and stage of cancer at the time of SARS-CoV-2 infection, prior and current anti-cancer therapy, presenting symptoms at SARS-CoV-2 diagnosis and severity, routine blood tests at SARS-CoV-2 diagnosis (routine biochemistry, full blood count), radiologic data at diagnosis and follow up data (admission to intensive care, anti SARS-CoV-2-specific therapy, complications from SARS-CoV-2 infection).

Data collection will be completely solely by members of the patients' team. Resulting clinical data will be fully anonymised and stored in a password-protected NHS computer.

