4.1.1 Inclusion criteria

The investigators will evaluate and include consecutive patients observed in the outpatients and inpatients facility of the study centre meeting all the following CRITERIA:

Inclusion criteria:

1. Be ≥ 18 years of age.
2. Have a confirmed diagnosis of malignancy of any type.
3. Have a confirmed diagnosis of SARS-CoV-2 infection.

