5.0 STATISTICAL ANALYSIS

5.1 Subject numbers.

5.1.1 Sample size.

For this observational, retrospective study, we propose a sample size of 5000 patients. Given the descriptive nature of this study no formal hypothesis testing is required. We will be retrospectively including patients fulfilling eligibility criteria between 1st January 2020 and 1st of April 2020.

5.2 Statistical methods.

Analysis of overall survival (OS) will validate the prognostic value of each clinico-pathologic trait collected at treatment initiation. Univariable analysis of survival will be used to derive median OS and associated 95% CI by using Kaplan-Meier methods and Log-rank tests.

The HRs and their associated CIs for OS will be computed using unadjusted and adjusted Cox proportional hazards models. We will employ a backward stepwise conditional model where each variable with an entry threshold of $p<0.05$ and an exit threshold of $p<0.10$ at each iteration. Proportional hazards will be adjusted for factors including active anticancer treatment type and features reflective of SARS-CoV-2 infection. Receiver-operating characteristics curve (ROC) will be used to test each variable for the accuracy of prediction of mortality at landmark survival endpoints (ie. 8, 12 weeks).

To test the predictive accuracy of each candidate prognostic variable we will use Harrell's rms packages to identify a subset of predictors by backward elimination, estimating the confidence intervals of the c-index statistics via bootstrapping (150 iterations).

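### The plan contradicts itself on the number of sites; if more than one NHS trust contributes, nothing in the listed data or models separates site from prognosis

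*Combined protocol and SAP*

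**What the plan says.** On the number of sites, three places disagree. The synopsis gives the number of study centres as 1. Section 4.1.1 takes "consecutive patients observed in the outpatients and inpatients facility of the study centre". Section 7.5, on sponsorship, says: "Delegated responsibilities will be assigned to the NHS trusts taking part in this study".

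On the data, Section 3.2 says: "The database consists of a Microsoft Excel spreadsheet including the following variables: age, gender, smoking status, prior comorbidities", and continues with cancer history, therapy, presenting symptoms, blood tests, radiology and follow-up. No trust, hospital or centre field is named.

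On the analysis, Section 5.2 plans Kaplan-Meier curves and log-rank tests, and then: "The HRs and their associated CIs for OS will be computed using unadjusted and adjusted Cox proportional hazards models". It adds: "Proportional hazards will be adjusted for factors including active anticancer treatment type and features reflective of SARS-CoV-2 infection". Stratification, a site term, a frailty and a clustered variance are not mentioned.

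**The concern.** An unstratified log-rank test or Cox model treats all patients as sharing one baseline hazard. Suppose several trusts contribute, their underlying mortality differs, and a factor such as active anticancer treatment is more common in some trusts than in others. The estimated hazard ratio then mixes prognosis within a trust with differences between trusts.

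Prognostic factors for survival are the second endpoint in Section 3.1, so these hazard ratios are a main output of the study. If site is not recorded at data entry, adjusting for it afterwards becomes harder.

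**Working it through.** **1. The plan's own figure.** The only planning number is the sample size: "For this observational, retrospective study, we propose a sample size of 5000 patients". Section 5.1.1 explains: "Given the descriptive nature of this study no formal hypothesis testing is required". No alpha, power, effect size or event rate is given, so the 5000 is a target that cannot be recomputed. The documents also give no number of trusts, no mortality by trust and no factor frequency by trust. Every input to steps 2 and 3 other than the 5000 patients and the 12-week landmark is therefore an assumption.

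**2. Approximate bias with many trusts, unadjusted model.** For a binary factor, the bias in the log hazard ratio is about Cov(factor, trust log-hazard) / Var(factor) = r × SD(share) × SD(log-hazard) / [p(1 − p)]. Here *share* is the proportion of a trust's patients with the factor.

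Assumptions: p = 0.5, so p(1 − p) = 0.25; SD of trust log-hazards 0.2 to 0.3; SD of trust shares 0.10 to 0.15; correlation r from −0.3 to −0.5. True hazard ratio 1.

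- Mild end: −0.3 × 0.10 × 0.2 / 0.25 = −0.024, hazard ratio 0.976.
- Strong end: −0.5 × 0.15 × 0.3 / 0.25 = −0.090, hazard ratio 0.914.

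The sign follows from the assumed negative correlation; a positive one would push the hazard ratio above 1. With SE = 2/√deaths, the rejection rate of a nominal 5% test is the probability that a N(bias/SE, 1) variable lies beyond ±1.96:

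| Deaths (assumed) | SE | Mild end | Strong end |
|---|---|---|---|
| 300 | 0.115 | 5.5% | 12% |
| 1500 | 0.052 | 8% | 41% |

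**3. Simulation with two trusts.** Assumptions: 5000 patients, two trusts of equal expected size, exponential survival, censoring at 12 weeks, 12-week mortality about 25%, mean factor prevalence 30%, 1000 replicates per scenario. True hazard ratio of the factor 1.00:

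| Trust hazard ratio | Prevalence difference (points) | Unstratified HR | 95% CI coverage | Stratified HR |
|---|---|---|---|---|
| 1.5 | 0 | 1.00 | 96% | 1.00 |
| 1.5 | 10 | 1.05 | 88% | 1.00 |
| 1.5 | 20 | 1.10 | 65% | 1.00 |
| 1.5 | 40 | 1.20 | 15% | 0.99 |
| 2.0 | 0 | 1.00 | 95% | 1.00 |
| 2.0 | 10 | 1.08 | 75% | 1.00 |
| 2.0 | 20 | 1.17 | 24% | 1.00 |
| 2.0 | 40 | 1.36 | 0% | 1.00 |

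With a true hazard ratio of 1.25 the pattern is the same. At equal prevalence the unstratified estimate is 1.24 to 1.25. At a 20-point difference it is 1.37 (trust hazard ratio 1.5) or 1.46 (trust hazard ratio 2.0). With a single centre the estimates are 1.00 and 1.25. Stratified models give 0.99 to 1.00 and 1.25, with coverage of 94 to 96% throughout.

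**4. Cross-check.** For a trust hazard ratio of 1.5 and a 10-point difference, the step 2 formula gives 0.05 × (ln 1.5 / 2) / (0.3 × 0.7) = 0.05 × 0.203 / 0.21 = 0.048, hazard ratio 1.05, which agrees with the simulation.

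**The case against.** The strongest objection is that a reader might infer from Section 7.5 that patients from several trusts will be analysed as one sample. No section says so. The sentence concerns delegated responsibilities; the synopsis and Section 4.1.1 give one centre, the data sit on one NHS computer (Sections 3.2 and 6.0), and one hospital office runs the study (Section 8.0). This stands, and it makes the point conditional. In the other direction, 5000 patients with both diagnoses between 1 January and 1 April 2020 is a large number for one centre, since Section 1.1 dates the pandemic declaration to 11 March. That is inference, not evidence of several sites.

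A reader might also infer that mortality differences between trusts bias the hazard ratios by themselves. The equal-prevalence rows show that they do not, and coverage there stays near 95%.

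Third, the calculations are for an unadjusted hazard ratio. Age, comorbidities, stage, severity and blood tests are collected, and adjusting for them may remove part of any site effect. This stands.

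Fourth, it is tempting to say that the omission could never be repaired. Section 3.2 calls the data fully anonymised, but Section 7.3 gives each patient a reference number and keeps source documents open to the sponsor, so site might be recoverable. Both the variable list and the adjustment list are open-ended, and not every page of the document was available for this check. Site is therefore unmentioned, not ruled out.

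Finally, a frailty or fixed site effects would also be defensible. Stratification is one sound choice among several, and by itself it does not address the ROC and c-index analyses.

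**Conclusion.** The point holds in conditional form. The documents contradict themselves on the number of sites. If more than one trust contributes, the analysis as written leaves the hazard ratios of factors whose frequency differs by trust open to confounding by site. Both conditions are needed: different mortality and different factor frequency.

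The size cannot be derived from the documents. Under the assumptions of step 2, a null factor appears with a hazard ratio of about 0.91 to 0.98 before adjustment. The 41% false-positive rate combines the strongest value of every assumption with 1500 deaths, so it should not be read as an estimate for this study. At the mild end, with 300 deaths, the effect is negligible (5.5% against 5%). The case for the change rests on its low cost and on its being harmless with one centre.

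**What to change.** - Reconcile the synopsis, Section 4.1.1 and Section 7.5 so that they give the same number of sites.
- Add a coded, pseudonymised trust or hospital field to the database in Section 3.2.
- In Section 5.2, state that if more than one site contributes, the log-rank tests and Cox models will be stratified by site (separate baseline hazards), with sites that have very few deaths combined.

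The cost is one extra column, one stratification term and a slight loss of precision when sites are small. No new patients or procedures are needed. With a single site the analysis is unchanged.

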7.6 Audits

The study may be subject to inspection and audit by Imperial College London under their remit as sponsor and other regulatory bodies to ensure adherence to GCP and the UK Policy Frame Work for Health and Social Care Research.

7.8 Publication Policy

A whole or part of the study results will be communicated, orally presented, and/or published in appropriate scientific journals. Full anonymity of subject's details will be maintained throughout. Subjects wanting to see the results of the trial can request a copy of the article from the investigators once it has been published.

8.0 STUDY MANAGEMENT

The day-to-day management of the study will be co-ordinated through the Cancer Research office at Hammersmith Hospital.

